5.1 SAFETY PLAN

The safety plan for patients in this study is based on clinical experience with venetoclax as well as atezolizumab plus carboplatin and etoposide in completed and ongoing studies. The anticipated important safety risks are outlined below (see Sections 5.1.1-5.1.4).

Measures will be taken to ensure the safety of patients participating in this study, including the use of stringent inclusion and exclusion criteria and close monitoring of patients during the study. Administration of venetoclax and atezolizumab plus carboplatin etoposide will be performed in a monitored setting in which there is immediate access to trained personnel and adequate equipment and medicine to manage potentially serious reactions. Guidelines for managing patients who experience anticipated adverse events, including criteria for dosage modification and treatment interruption or discontinuation, are provided in Appendix 10, Appendix 11, Appendix 12, and Appendix 13. Refer to Sections 5.2–5.7 for details on safety reporting (e.g., adverse events, pregnancies) for this study.

5.1.1 Risks Associated with Atezolizumab

Atezolizumab has been associated with risks such as the following: IRRs and immunemediated hepatitis, pneumonitis, colitis, pancreatitis, diabetes mellitus, hypothyroidism, hyperthyroidism, adrenal insufficiency, hypophysitis, Guillain-Barré syndrome, myasthenic syndrome or myasthenia gravis, meningoencephalitis, myocarditis, nephritis, and myositis. Immune-mediated reactions may involve any organ system and may lead to hemophagocytic lymphohistiocytosis and macrophage activation syndrome. Refer to Appendix 13 of the protocol and Section 6 of the Atezolizumab Investigator's Brochure for a detailed description of anticipated safety risks for atezolizumab.

5.1.2 Risks Associated with Etoposide

Etoposide is known to cause bone marrow suppression including myelosuppression, anemia, thrombocytopenia, gastrointestinal symptoms (e.g., nausea, vomiting, diarrhea), hepatotoxicity, and alopecia. Etoposide-based chemotherapy is considered to be moderately emetogenic. Etoposide carries a risk of secondary hematologic malignancy. Patients will be monitored for etoposide-related adverse events.

For more details regarding the safety profile of etoposide, refer to the etoposide prescribing information.

5.1.3 Risks Associated with Carboplatin

Carboplatin is known to cause bone marrow suppression including myelosuppression, anemia, and thrombocytopenia. Carboplatin-based chemotherapy is considered to be moderately emetogenic. Patients will be monitored for carboplatin-related adverse events.

Venetoclax—F. Hoffmann-La Roche Ltd Page 106 of 214 Protocol GO41864, Version 2 For more details regarding the safety profile of carboplatin, refer to the carboplatin prescribing information.

5.1.4 Risks Associated with Venetoclax

Clinical experience gained thus far with venetoclax has demonstrated that it is generally well tolerated, and toxicities appear to be mostly manageable and/or reversible; see the Venetoclax Investigator's Brochure for more information.

On the basis of clinical data to date, the following known and potential risks with venetoclax are described below. Guidelines around the management of these risks through dose and schedule modifications are described in Section 5.1.5.1.

5.1.4.1 Tumor Lysis Syndrome

Available data suggest that in patients with non-CLL, with the exception of those with mantle cell lymphoma, the risk of TLS is low with venetoclax. Due to different biology between ES-SCLC and hematological malignancies, the risk of TLS is considered to be low in patients with ES-SCLC.

Nevertheless, patients should be advised to remain well hydrated for the first week of study drug administration. Although not mandatory, at the discretion of the investigator, a prophylactic oral agent (e.g., allopurinol 300 mg QD) may be initiated in patients who are deemed to be at the risk of TLS in order to reduce the uric acid level. Laboratory values obtained before the dose of venetoclax are to be used to determine whether a patient developed a change related to TLS. Laboratory results of the 24-hour postdose must be reviewed before receiving the dose of venetoclax for that day. Patients who develop electrolyte changes suggestive of TLS should undergo aggressive management and further monitoring per Appendix 11.

Patients with TLS should be treated as per institutional practice and local guidelines, including correction of electrolyte abnormalities and monitoring of renal function and fluid balance. Recommendations for initial management of electrolyte imbalances and prevention of TLS are provided in Appendix 11. In some cases, dialysis may be indicated. Guidelines for defining TLS are provided in Appendix 9.

5.1.4.2 Neutropenia

Neutropenia is an important identified risk for venetoclax. Clinical data from the oncology studies suggest that the neutropenia adverse events are observed among subjects who receive venetoclax as a single agent or in combination with other therapeutic agents, with higher frequency observed in some combination studies. Serious adverse events of neutropenia or neutropenia events that lead to discontinuations are few across the entire venetoclax oncology program. Neutropenia management guidelines are provided in Table 10 and Appendix 12. Granulocyte colony stimulating factors are permitted according to local practice, and patients will be monitored and treated promptly in case of infection.

Venetoclax—F. Hoffmann-La Roche Ltd Page 107 of 214 Protocol GO41864, Version 2
5.1.4.3 Serious Infections

Serious infection is an important identified risk for venetoclax. Infections have been reported in the oncology clinical studies; however, these events are confounded by the underlying disease, comorbidities, and other immunosuppressive medications. To date, no clear relationship has been noted between serious infectious events and neutropenia. The types of infectious events observed generally have been consistent with those anticipated in the elderly population of heavily pretreated subjects with hematologic malignancies and are similar across all indications. Infections are closely monitored in venetoclax program across all indications. Patients should be advised to report fever and should be assessed for further management as per standard medical practice. In the oncology studies, recommendations are included in the protocol regarding the need for anti-infective prophylaxis per standard of care (e.g., NCCN for oncology subjects).

5.1.4.4 Other Hematological Effects

Anemia has been reported across oncology studies investigating venetoclax, with a higher frequency in some studies in which venetoclax is combined with other reference therapies; however, most of the events were non-serious and confounded by disease factors and prior therapies.

Thrombocytopenia adverse events have been reported in oncology studies investigating venetoclax, with a higher frequency in those studies in which venetoclax was combined with other chemotherapeutic agents. However, most of the events were non-serious and assessment of these events is confounded by the patients' underlying hematologic malignancy disease state, prior therapies, and preexisting thrombocytopenia, including autoimmune thrombocytopenia in several patients.

Lymphopenia has been observed in nonclinical studies and in the phase I clinical study conducted in heavily pretreated patients with CLL and NHL. While opportunistic infections have been reported in the clinical program, data are confounded by the patients' underlying disease and prior therapies. Patients in this study who develop lymphopenia are potentially at risk for atypical infections. As such, prophylaxis against varicella zoster virus and *Pneumocystis jiroveci* pneumonia should be considered and implemented (if applicable) as per local institutional practice

5.1.4.5 Reproductive System Effects and Pregnancy

This study enrolls both male and female patients. The effect of Bcl-2 inhibition on pregnancy has not been fully characterized. In animal studies, venetoclax resulted in increased post implantation loss, and decreased fetal body weights were observed in the mouse embryo-fetal development study at the highest dosage administered. Venetoclax was not teratogenic. Two human pregnancies have been reported in the clinical program with venetoclax so far, including one pregnancy of a partner; in both cases, a live infant with no neonatal complication, congenital anomalies, or birth defects was delivered.

Venetoclax—F. Hoffmann-La Roche Ltd Page 108 of 214 Protocol GO41864, Version 2 In nonclinical studies, venetoclax has shown a potential to cause reproductive and embryo-fetal developmental toxicities as single agent. No reproductive or teratogenicity studies in animals have been conducted with atezolizumab. The PD-L1/PD-1 signaling pathway is well established as essential in maternal/fetal tolerance and embryo-fetal survival during gestation. Administration of atezolizumab is expected to have an adverse effect on pregnancy and poses a risk to the human fetus, including embryo lethality. Consequently, both venetoclax and atezolizumab should not be administered to pregnant women, and they must be discontinued if a patient becomes pregnant. Additionally, patients are advised to remain abstinent (i.e., refrain from heterosexual intercourse) or use non-hormonal contraceptive methods with a failure rate of <1% per year during the treatment period and for 30 days after the last dose of study drug. Please refer to Section 4.1.1 for further details on study eligibility and contraceptive requirements for patients.

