Patients with documented bone or liver metastases: alkaline phosphatase \leq 5 \times ULN

- Serum total bilirubin $\leq 1.5 \times ULN$

Patients with known Gilbert disease who have serum bilirubin level \leq 3 \times ULN may be enrolled.

- Albumin ≥ 25 g/L (2.5 g/dL)

 Creatinine clearance (CRCL) ≥ 50 mL/min calculated with the use of the 24-hour CRCL or modified Cockcroft-Gault equation (i.e., estimation of creatinine clearance rate [eCCr]) with the use of ideal body mass (IBM) instead of mass:

> eCCr = $(140 - age) \times (weight in kg) \times (0.85 \text{ if female})$ 72 × (serum creatinine in mg/dL)

Or, if serum creatinine is in μ mol/L:

 $eCCr = (140 - age) \times IBM (kg) \times (1.04 \text{ if female})$

serum creatinine (µ mol/L)

- Patients must submit a pre-treatment tumor tissue sample. Any available tumor tissue sample can be submitted (fresh, paraffin-embedded tissue block, or serial cut slides [15 preferred]). The tissue sample should be submitted before or within 4 weeks after enrollment; however, patients may be enrolled into the study before the pre-treatment tumor tissue sample is submitted. If tissue is not available, approval from the Medical Monitor is required before enrolling.
- Patients must submit a blood sample for exploratory biomarker research before treatment, on-study, and following progression of disease.
- For women of childbearing potential: agreement to remain abstinent (refrain from heterosexual intercourse) or use non-hormonal contraceptive methods that result in a failure rate of < 1% per year during the treatment period and for at least 30 days after the final dose of venetoclax, 5 months after the final dose of atezolizumab, or 6 months after the final dose of carboplatin or etoposide, whichever is longer. Women must refrain from donating eggs during this same period.

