- Patients must submit a pre-treatment tumor tissue sample. Any available tumor tissue sample can be submitted (fresh, paraffin-embedded tissue block, or serial cut slides [15 preferred]). The tissue sample should be submitted before or within 4 weeks after enrollment; however, patients may be enrolled into the study before the pre-treatment tumor tissue sample is submitted. If tissue is not available, approval from the Medical Monitor is required before enrolling.
- Patients must submit a blood sample for exploratory biomarker research before treatment, on-study, and following progression of disease.

Venetoclax—F. Hoffmann-La Roche Ltd Page 70 of 214 Protocol GO41864, Version 2 For women of childbearing potential: agreement to remain abstinent (refrain from heterosexual intercourse) or use non-hormonal contraceptive methods that result in a failure rate of <1% per year during the treatment period and for at least 30 days after the final dose of venetoclax, 5 months after the final dose of atezolizumab, or 6 months after the final dose of carboplatin or etoposide, whichever is longer. Women must refrain from donating eggs during this same period.

A woman is considered to be of childbearing potential if she is postmenarchal, has not reached a postmenopausal state (≥ 12 continuous months of amenorrhea with no identified cause other than menopause), and is not permanently infertile due to surgery (i.e., removal of ovaries, fallopian tubes, and/or uterus) or another cause as determined by the investigator (e.g., Müllerian agenesis). The definition of childbearing potential may be adapted for alignment with local guidelines or regulations.

Examples of contraceptive methods with a failure rate of < 1% per year include bilateral tubal ligation, male sterilization, hormonal contraceptives that inhibit ovulation, hormone-releasing intrauterine devices, and copper intrauterine devices.

Hormonal contraceptive methods must be supplemented by a barrier method.

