Diarrhea, Grade 4	 Withhold venetoclax. Withhold atezolizumab plus carboplatin etoposide. Administer anti-diarrheals per institutional guidelines (e.g., loperamide 4 mg initial dose up to a maximum of 16 mg per day) Upon resolution of Grade 4 diarrhea to Grade ≤ 1: Resume treatment with venetoclax at one dose level reduction (see Table 7) Administer carboplatin and etoposide at 75% of previous dose (see Table 8). Dose of carboplatin and etoposide can be re-escalated (even to full dose) with the approval of Medical Monitor (see Section 5.1.5.2). Administer atezolizumab at previous dose. For uncontrolled Grade 4 diarrhea that occurs despite adequate anti-diarrhea medication or any grade of diarrhea requiring hospitalization: Further reduce venetoclax by one dose level (see Table 7). Administer carboplatin and etoposide at 75% of previous dose (see Table 8).
Hepatic event, Grade 2	 Monitor LFTs more frequently until return to baseline Events of > 5 days duration: Withhold atezolizumab for up to 12 weeks after event onset. Initiate treatment with corticosteroids equivalent to 1–2 mg/kg/day oral prednisone. If event resolves to Grade 1 or better, resume atezolizumab. If event does not resolve to Grade 1 or better while withholding atezolizumab, permanently discontinue atezolizumab and contact Medical Monitor.

Table 10Management Guidelines for Specific Adverse Events with
Venetoclax, Atezolizumab, and Carboplatin Etoposide (cont.)

Table 10 Management Guidelines for Specific Adverse Events with Venetoclax, Atezolizumab, and Carboplatin Etoposide (cont.)

Event	Management	
Hepatic event, Grade 3	 Discontinue atezolizumab. Withhold venetoclax. Withhold carboplatin and etoposide. If hepatic event resolves to ≤ Grade 1: Resume venetoclax at one dose level reduction (see Table 6). Administer carboplatin and etoposide at 75% of previous dose (see Table 8). 	
Hepatic event, Grade 4	Discontinue atezolizumab.Discontinue venetoclax.Discontinue carboplatin and etoposide.	

ANC = absolute neutrophil count; G-CSF = growth-colony stimulating factor.

^a Dose modifications (as specified in the table above) should be made based on ANC and platelet count assessment on Day 1 of each cycle. No dose modifications are required based on ANC and platelet count assessment done on Cycle 1, Day 8 and Cycle 1, Day 15.

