Female patients of childbearing potential will be instructed to immediately inform the investigator if they become pregnant during the study or within 30 days after the final dose of venetoclax, 5 months after the final dose of atezolizumab, or 6 months after the final dose of carboplatin or etoposide, whichever occurs last. A paper Clinical Trial Pregnancy Reporting Form should be completed and submitted to the Sponsor or its designee immediately (i.e., no more than 24 hours after learning of the pregnancy). either by faxing or by scanning and emailing the form using the fax number or email address provided to investigators. Pregnancy should not be recorded on the Adverse Event eCRF. The investigator should discontinue study treatment and counsel the patient, discussing the risks of the pregnancy and the possible effects on the fetus. Monitoring of the patient should continue until conclusion of the pregnancy. Any serious adverse events associated with the pregnancy (e.g., an event in the fetus, an event in the mother during or after the pregnancy, or a congenital anomaly/birth defect in the child) should be reported on the Adverse Event eCRF. In addition, the investigator will submit a Clinical Trial Pregnancy Reporting Form when updated information on the course and outcome of the pregnancy becomes available.

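### Section 5.1.4.5 gives a 30-day contraception period where Section 4.1.1 requires months more, and the synopsis and 4.1.1 criterion contradicts itself on hormonal methods

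*Combined protocol and SAP*

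**What the plan says.** **Duration.** Section 5.1.4.5 sits under Section 5.1.4, which announces that "the following known and potential risks with venetoclax are described below". Its second paragraph is wider than that: it describes the reproductive toxicity of venetoclax, says that atezolizumab is expected to endanger the fetus (embryo lethality included), and bars both drugs in pregnancy. It then advises patients to abstain or use non-hormonal contraception "during the treatment period and for 30 days after the last dose of study drug". The next sentence reads "Please refer to Section 4.1.1 for further details on study eligibility and contraceptive requirements for patients".

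The eligibility criterion for women in Section 4.1.1 sets three periods: 30 days after the final venetoclax dose, "5 months after the final dose of atezolizumab, or 6 months after the final dose of carboplatin or etoposide, whichever is longer". The synopsis states the same rule ("for at least 30 days after the final dose of venetoclax, 5 months after the final dose of atezolizumab", and so on). Section 5.4.3.1, on reporting pregnancies in female patients, uses the same three periods ("within 30 days after the final dose of venetoclax, 5 months after the final dose of atezolizumab", then 6 months for chemotherapy).

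**Method.** The 4.1.1 criterion asks women to abstain "or use non-hormonal contraceptive methods that result in a failure rate" below 1% per year. The explanatory text under that criterion lists ovulation-inhibiting hormonal contraceptives and hormone-releasing intrauterine devices among the acceptable examples, and requires a barrier with any hormonal method. The synopsis does the same. Section 4.4.1 lists oral contraceptives as permitted therapy and refers back to 4.1.1.

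**The concern.** The period in 5.1.4.5 equals the shortest of the three terms in 4.1.1, yet it is stated for the study drug in a paragraph that has just described fetal harm from atezolizumab. A site working from that sentence could give a woman a stop date months before the one she agreed to at enrolment. The possible harm is fetal exposure to a drug that the same paragraph links to embryo lethality.

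The point on method concerns an eligibility criterion, and Section 9.2 does not allow eligibility waivers. Faced with a woman using an oral contraceptive plus a barrier, one site could exclude her on the requirement and another could enrol her on the examples beneath it. No endpoint, sample size or analysis depends on either point.

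**Working it through.** The protocol states no figure for the difference, so there is none to reproduce. The check is date arithmetic.

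**Inputs**
- Periods: 30 days, 5 months and 6 months, the longest applying (4.1.1); 30 days after the last dose (5.1.4.5).
- Maintenance: atezolizumab on Day 1, venetoclax on Days 1–21 of a 21-day cycle (3.1.2.1).
- Induction: atezolizumab and carboplatin on Day 1, etoposide on Days 1–3, venetoclax on Days 1–7 or 1–14 (3.1.2.2).
- Month length (assumption): 30.44 days, so 5 months = 152 days and 6 months = 183 days.
- No delay between cycles (assumption): the last etoposide dose is then 22 − 3 = 19 days before Day 1 of maintenance Cycle 1.

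**Formula.** Let Day 1 be Day 1 of the last atezolizumab cycle. Gap = (latest of last venetoclax + 30, last atezolizumab + 152, last chemotherapy + 183) − (last dose + 30).

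**All planned doses of the last cycle taken**

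| Last cycle | 4.1.1 ends | 5.1.4.5 ends | Gap |
|---|---|---|---|
| Maintenance Cycle 2 or later | Day 1 + 152 = 153 | 21 + 30 = 51 | 102 days (3.4 months) |
| Maintenance Cycle 1 after induction | 1 − 19 + 183 = 165 | 51 | 114 days (3.7 months) |
| Induction, venetoclax to Day 14 | 3 + 183 = 186 | 14 + 30 = 44 | 142 days (4.7 months) |
| Induction, venetoclax to Day 7 | 186 | 7 + 30 = 37 | 149 days (4.9 months) |

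By maintenance Cycle 2 the chemotherapy term ends on Day 1 − 40 + 183 = 144, before Day 153, so atezolizumab governs from there on.

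**Dosing cut short within the cycle**
- Atezolizumab on Day 1 is the last drug given: 153 − 31 = 122 days (4.0 months) from maintenance Cycle 2 on; 165 − 31 = 134 days (4.4 months) in maintenance Cycle 1.
- Every drug stopped by Day 3 of an induction cycle: 186 − 33 = 153 days (5.0 months).

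**Venetoclax continued after atezolizumab stops.** Table 10 allows this after a Grade 3 hepatic event: atezolizumab is discontinued, and venetoclax may restart one dose level lower on the condition "If hepatic event resolves to ≤ Grade 1". In maintenance, ignoring any hold, the gap after n further full cycles is max(0, 153 − [21(n + 1) + 30]). For n = 0 to 5 this gives 102, 81, 60, 39, 18 and 0 days. The gap is zero once the last venetoclax dose is 122 or more days after the last atezolizumab dose (1 + 122 + 30 = 153).

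**Sensitivity to month length.** With months of 30 and 31 days, the full maintenance cycle gives 100 and 105 days, and induction with venetoclax to Day 7 gives 146 and 152 days. The conclusion does not change.

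**Method wording, side by side**
- Requirement in the synopsis, 4.1.1 and 5.1.4.5: non-hormonal.
- Examples and barrier sentence in the synopsis and 4.1.1: hormonal methods acceptable with a barrier.
- 4.4.1: oral contraceptives permitted.

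Section 5.1.4.5 therefore agrees with the requirement sentence of 4.1.1. The conflict lies within the criterion itself, and between the requirement and 4.4.1.

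**The case against.** The strongest defence is that study drug in 5.1.4.5 means venetoclax. The subsection belongs to the venetoclax risks, Section 5.1.4.1 uses the term in its hydration advice on tumor lysis, and Appendix 12 (the venetoclax guideline) uses it for resuming treatment. On that reading the 30 days is simply the venetoclax term of 4.1.1, and the sentence is incomplete but does not contradict the rule. The reading is possible but strained: the paragraph has just covered both drugs, and Section 4.3.2.3 uses the term for either one. It also leaves the planned-dose gaps unchanged, because venetoclax is the last drug taken in every completed cycle.

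A second defence is that the full rule is already in place. The next sentence points to 4.1.1, every woman must agree to that criterion before enrolment, and 5.4.3.1 repeats the periods. This stands as mitigation. It does not correct the number, because the cross-reference presents 4.1.1 as further detail and does not say that it overrides the 30 days. Nor can one infer that women will actually be told the wrong date: the consent form is not available here.

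On method, a reader might infer that non-hormonal is plainly the slip, since the examples, the barrier sentence and 4.4.1 all point the other way. The documents do not settle this. Those passages could equally be leftover text, and non-hormonal is the stricter rule.

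**Conclusion.** Both inconsistencies are real, and both are matters of wording. The 4.1.1 durations are not in question.

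On duration, the 5.1.4.5 sentence falls short of the binding rule by 3.4 to 4.9 months when the last cycle is completed as planned. A reader might infer a shortfall of 5.0 months on planned schedules. The documents do not support that, because it needs every drug to stop by Day 3 of an induction cycle while planned venetoclax runs to Day 7 or 14. Even the 4.7–4.9 month range describes treatment that ends in induction. For a woman who goes on to at least two maintenance cycles the figure is 3.4 months, and it can shrink to zero if venetoclax outlasts atezolizumab.

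The protocol does not give the number of women of childbearing potential. Assuming 0 to 3 of the approximately 62 patients, the practical exposure is small and may be nil.

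On method, the criterion cannot be applied as written, although the barrier sentence gives sites a workable rule until it is settled.

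A reader might also see an error in the provisions for men, whose contraception period in 4.1.1 follows chemotherapy only while 5.4.3.2 has partner pregnancies reported over all three windows. That does not follow: a reporting window is surveillance and need not equal the contraception period.

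The matter merits correction at the next amendment because the subject is fetal safety and the remedy costs almost nothing.

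**What to change.** 1. In 5.1.4.5, replace the 30-day wording with the drug-by-drug rule of 4.1.1, or delete it and keep only the reference to 4.1.1. Either change reduces the gap to zero.
2. Have the sponsor choose one rule on hormonal methods and apply it in the synopsis, 4.1.1, 4.4.1 and 5.1.4.5. If hormonal methods with a barrier are intended, delete non-hormonal from the synopsis, 4.1.1 and 5.1.4.5 and keep the barrier requirement. If only non-hormonal methods are intended, delete the hormonal examples and the barrier sentence from the synopsis and 4.1.1, and the oral-contraceptive entry from 4.4.1.
3. Check that the consent form matches.

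The cost is a few lines of text in at most four places, with no new visit, procedure or analysis.
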